1.2.6.2. Safety Outcome Measures

Safety will be assessed through the evaluation of AEs, 12-lead electrocardiograms (ECGs), radiologic tests, vital signs (temperature, heart rate, blood pressure, and respiratory rate), and clinical laboratory evaluations (hematology and coagulation evaluations, chemistry panel, and urinalyses).

CONFIDENTIAL Page 25 of 56

2. SUBJECT POPULATION

2.1. Population Definitions

The following analysis populations will be evaluated and used for presentation and analysis of the data:

- Intent-to-Treat (ITT) Population: All subjects randomized to treatment. A subject is considered randomized when a randomization transaction has been recorded in the IWRS, regardless of whether the subject actually receives study drug.
- Safety Population: All subjects randomized to treatment and who received any amount of study drug.
- Microbiological Intent-to-treat Population (mITT): A subset of subjects in the Safety population with documented *Candida* infection based on a Central Laboratory evaluation of an isolate from a blood culture obtained within 96 hours of randomization or from a specimen obtained from a normally sterile site. Determination of the identification of fungal pathogens will follow the process defined in SAP Section 4.
- Microbiological Intent-to-treat 2 Population (mITT2): A subset of subjects in the mITT population had documented *Candida* infection based on Central Laboratory evaluation of:
 - o a culture from blood drawn within 12 hours prior to randomization or within 72 hours after randomization; OR
 - o a culture from another normally sterile site obtained within 48 hours prior to randomization or within 72 hours after randomization.
- Microbiological Intent-to-treat 3 Population (mITT3): A subset of subjects in the mITT population who had documented *Candida* infection based on Central Laboratory evaluation of:
 - o a culture from blood drawn within 12 hours prior to randomization or within 72 hours after randomization; OR
 - o a culture from another normally sterile site obtained within 96 hours prior to randomization or within 72 hours after randomization.
- Pharmacokinetics (PK) Population: All CD101 treated subjects with at least 1 plasma sample obtained for PK analysis.

Demographics (including age, race, and gender), diagnosis (candidemia and/or IC), medical history, baseline assessments, mycological data, systemic signs and symptoms, and administration of study drug will be summarized for the ITT population, unless otherwise specified. The Safety population is the primary population for the analysis of safety endpoints. All efficacy analyses will be conducted in the mITT population, unless otherwise specified. A select set of efficacy analysis will also be perfomed in the mITT2 and mITT3 populations.

2.2. Protocol Deviations

Protocol deviations are defined as any variation from the protocol, including enrollment of a subject who did not meet all inclusion and exclusion criteria and failure to perform the assessments and procedures within the required time frame. Protocol deviations, will be categorized into types of deviations, and classified as major or minor.

CONFIDENTIAL Page 26 of 56

The Sponsor or designee will be responsible for producing the final protocol deviation file (formatted as a Microsoft Excel file), in collaboration with Veristat and the data monitoring group as applicable. This file will be finalized prior to hard database lock.

CONFIDENTIAL Page 27 of 56

3. GENERAL STATISTICAL METHODS

3.1. Sample Size Justification

This is an exploratory study and therefore, is not powered for inferential statistical analyses. A sufficient number of subjects are randomized to the CD101 IV and IV caspofungin treatment groups in Part A to provide an initial, substantive analysis of safety, tolerability, and estimate efficacy.

It is expected that approximately 114 subjects in Part A will need to be randomized given an estimated discontinuation rate of 20%, in order to achieve 90 evaluable subjects in the mITT population. In Part A, assuming a 73% overall success rate, the sample size of 30 subjects in the mITT population in each CD101 IV treatment group and the IV Caspofungin group will yield a 95% confidence interval (CI) for this success rate of 53.8% to 87.5%.

The addition of Part B in Amendment 5 of the protocol increased the study sample size by approximately 50% to 130% (depending on the rate of enrollment over the additional months to the staged start of the Phase 3 study and the rolling close-out of Part B). In Part B, subjects will be randomized until there are at least 30 subjects in the CD101 IV treatment groups at any dose and 30 subjects in the comparator group (≥45 additional subjects and no more than 120 subjects). In Part B, total enrollment will depend on the enrollment rate for the period between the end of Part A and the start of the Phase 3 study. With the addition of Part B subjects and assuming a 73% overall success rate, a total approximate sample size of 60 subjects in the CD101 treatment group (consisting of Group 1 from Amendment 5 and Group 2 from Amendment 6) will yield a 95% CI of 60.0% to 83.7%, and a total approximate sample size of 110 subjects in the CD101 treatment group (consisting of Group 1 from Amendment 5 and Group 2 from Amendment 6) will yield a 95% CI of 63.7% to 81.0%.

3.2. General Methods

All tables, figures, and listings will be presented in landscape orientation in Courier New, 8-point font.

All tables, figures, and listings will be incorporated into Microsoft Word, or Adobe Acrobat PDF files, sorted and labeled according to the International Conference on Harmonisation (ICH) recommendations, and formatted to the appropriate page size(s).

All data listings and tables displaying by-subject data that contain an evaluation date will display a relative study day (Study Day). Study Day 1 is defined as the first day of study drug administration and subsequent study days are defined by the number of consecutive calendar days thereafter. The day prior to the first dose of study drug is Study Day -1; there is no Study Day 0.

If a clinical laboratory result is reported relative to a lower/upper range of detection for an assay, for example "<10," the numeric portion of the result (10) will be used for statistical analyses and the full result, including any symbols, will be provided in the subject listings.

Tabulations will be produced for appropriate demographic, baseline, efficacy, and safety parameters. Sample sizes shown with summary statistics are the number of subjects with non-missing values.

 Where individual data points are missing, categorical data will be summarized based on reduced denominators (ie, only subjects with available data will be included in the denominators).

CONFIDENTIAL Page 28 of 56

- For continuous variables, the number of subjects, mean, median, standard deviation (SD), minimum (min), and maximum (max) values will be presented.
- Time-to-event data will be summarized using Kaplan-Meier methodology using 25th, 50th (median), and 75th percentiles with associated 2-sided 95% CIs, as well as percentage of censored observations.
- Point estimates for overall response, mycological success and clinical success with exact 2-sided 95% CIs will be determined using the Clopper-Pearson method.

3.3. Computing Environment

All descriptive statistical analyses will be performed using SAS statistical software v9.3, unless otherwise noted. Medical history and AEs will be coded using the Medical Dictionary for Regulatory Activities (MedDRA) v19.0. Prior and concomitant medications will be coded using the World Health Organization (WHO) Drug Dictionary March 2016.

3.4. Baseline Definitions

For all analyses with exception of the analysis involving attributable systemic signs, baseline will be defined as the most recent measurement prior to the first administration of study drug. In the event the screening visit and treatment administration occur on the same date, baseline will be defined as measurements obtained at the screening visit.

All blood and normally sterile site samples taken 96 hours before randomization will be used to determine the presence of *Candida* at baseline. In instances where multiple samples of the same type occur with the same pathogen within 96 hours before randomization, the sample with highest MIC to study drug will be used as baseline pathogen.

For attributable systemic signs, all assessments of signs taken in the period 4 hours prior to the draw of the qualifying blood culture (when systemic signs of infection resulted in obtaining blood cultures), qualifying positive culture from a sterile site, or qualifying rapid IVD, through the first dose of study drug will be used to determine the presence of attributable systemic signs at baseline.

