Subjects randomized to the CD101 IV treatment group 1 will receive 1 dose of CD101 IV (400 mg) over 60 (±10) minutes on Day 1 and Day 8 and IV placebo on other study days in order to maintain the blind; subjects who require >14 days of IV therapy will receive an optional third dose of CD101 IV (400 mg) on Day 15. Subjects with IC are allowed an optional CD101 IV dose (400 mg) on Day 22 if additional therapy is required. Subjects in group 1 will receive IV placebo on other study days in order to maintain the blind. Subjects randomized to the CD101 IV treatment group 2 will receive 1 dose of CD101 IV (400 mg) over 60 (\pm 10) minutes on Day 1, 200 mg on Day 8 and IV placebo on other study days in order to maintain the blind; subjects who require >14 days of IV therapy will receive an optional third dose of CD101 IV (200 mg) on Day 15. Subjects with IC are allowed an optional CD101 IV dose (200 mg) on Day 22 if additional therapy is required. Subjects in group 2 will receive IV placebo on other study days in order to maintain the blind. Subjects may receive oral step-down therapy after ≥3 days of IV therapy, if criteria are met. Step-down therapy in both CD101 IV treatment groups will be oral placebo, in order to maintain the blind. Subjects who have already switched to oral step-down therapy will receive both oral placebo and CD101 IV on Day 8 and optional oral placebo and CD101 IV on Day 15 for subjects who require >14 days of therapy. Dosage adjustments are not allowed. Intravenous study drug is administered 24 (±2) hours after study drug was administered on the previous day.

Subjects randomized to the caspofungin group will receive IV caspofungin (70 mg loading dose on Day 1 and then 50 mg/day) for ≥ 3 days up to a maximum of 21 days for subjects with candidemia only or up to a maximum of 28 days for subjects with IC. After ≥ 3 days of IV therapy, subjects in the IV caspofungin group can be switched to oral step-down therapy if criteria are met. Step-down therapy in the caspofungin treatment group will be oral fluconazole (a loading dose of 800 mg [4 capsules] on the first day followed by 400 mg [2 capsules]/day thereafter). In order to maintain the blind, subjects who have already switched to oral step-down therapy will receive both oral fluconazole and IV placebo on Day 8, Day 15 for subjects who require ≥ 14 days of therapy. Intravenous study drug is administered 24 (± 2) hours after study drug was administered on the previous day.

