1.2.2. Randomization and Blinding

After informed consent has been obtained, subjects will be screened for study eligibility before randomization. Subjects in Part A will be assigned a subject number and randomized (1:1:1) to receive CD101 IV treatment group 1, CD101 IV treatment group 2, or caspofungin on Day 1 just prior to dosing. Subjects in Part B enrolled under Amendment 5 will be assigned a subject number and randomized (2:1) to receive CD1010 IV treatment group 1 or caspofungin on Day 1 just prior to dosing. Subjects in Part B enrolled under Amendment 6 will be assigned a subject number and randomized (2:1) to receive CD1010 IV treatment group 2 or caspofungin. Randomization will be stratified based on the method used at Screening to establish the diagnosis (blood culture/rapid in vitro diagnostic [IVD] and positive Gram stain/culture from a specimen obtained from a normally sterile site). If a subject has both a positive blood culture/rapid IVD and Gram stain/culture from a specimen obtained from a normally sterile site, the subject will be randomized within the positive Gram stain/culture from a specimen obtained from a normally sterile site stratum. The study site's pharmacist (or pharmacist designee) will obtain the study drug assignment from the IWRS. A subject is considered randomized when a randomization transaction has been recorded in the IWRS and the subject is assigned a randomization number.

All subjects and study personnel, including the Sponsor, Principal Investigator (PI), and site personnel involved in study conduct will remain blinded to by subject study medication assignment for both Part A and Part B until the study is completed and the database is locked, with the exception of the Pharmacy Monitor to monitor drug preparation and drug accountability during the study and cases in which unblinding is required due to a safety or tolerability issue. Additionally, in Part A only, some personnel including the PK analyst and an unblinded statistician, will be unblinded but will not be involved in the study conduct or the final analysis. An unblinded statistician will perform the analysis on the interim and final unblinded Part A data. To maintain study blinding, study drug preparation will be performed by an unblinded site pharmacist (or qualified unblinded personnel at the study site not involved with study procedures or evaluations).

CONFIDENTIAL Page 11 of 56

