Instructions for study drug preparation and dosing are outlined in the Pharmacy Manual provided separately to the site. In the case of a medical emergency requiring the PI to know the identity of the study drug, the PI will follow the procedures outlined in SAP Section 1.2.3.

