5.1.7. Baseline Fungal Pathogens

The genus and species of fungal pathogens identified from baseline blood cultures and normally sterile sites will be summarized by treatment group for subjects in the mITT population.

For each baseline *Candida* species, a summary of the distribution of minimum inhibitory concentration (MIC) results from the central lab (or if not available, from the local lab) will be presented both by treatment group and for treatment groups combined for subjects in the mITT population in separate tables for each of CD101, caspofungin, anidulafungin, micafungin, and fluconazole. In addition, for each baseline *Candida* species, the MIC₅₀, MIC₉₀, and MIC_{Range} for CD101, caspofungin, and fluconazole will be summarized, only where there are at least 10 of a particular *Candida* species with susceptibility data available from the central mycology laboratory in each treatment group, will be summarized both by treatment group and for treatment groups combined for subjects in the mITT population.

A by-subject listing will be provided displaying all MIC results for any baseline *Candida* species that is resistant to echinocandins; a separate by-subject listing will be provided displaying all MIC results for any baseline *Candida* species that is resistant to fluconazole.

CONFIDENTIAL Page 36 of 56

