5.3.3.3. Overall Success at Day 14 (± 1) by Baseline *Candida* species

The number and percentage of subjects programmatically determined to be an overall success (mycological eradication and resolution of clinical signs of candidemia) at Day 14 (± 1) will be summarized by baseline *Candida* spp. and treatment group for subjects in the mITT population.

Overall success by baseline *Candida* species and MIC cutoff for CD101, caspofungin and fluconazole at Day 14 (± 1) will be summarized by treatment group for subjects in the mITT population.

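### Among repeat same-type, same-species baseline samples, the SAP keeps the isolate with the highest MIC to the assigned drug, so the MIC tables compare differently selected isolates across arms

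*SAP*

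**What the plan says.** SAP Section 3.4 uses all blood and normally sterile site samples from the 96 hours before randomization to establish Candida at baseline. It then adds a rule for duplicates. The trigger is this: "In instances where multiple samples of the same type occur with the same pathogen within 96 hours before randomization". Which of the duplicates to keep is then settled by susceptibility, in these terms: "the sample with highest MIC to study drug will be used as baseline pathogen". No drug is named.

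Section 1.2.2 uses study drug for the allocated treatment: the pharmacist "will obtain the study drug assignment from the IWRS", and there is a procedure "In the case of a medical emergency requiring the PI to know the identity of the study drug". In Section 1.2.1 the comparator regimen has two active components, IV caspofungin and then a switch: "Step-down therapy in the caspofungin treatment group will be oral fluconazole".

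The MIC results are used in two places. Section 5.1.7 tabulates them by species "in separate tables for each of CD101, caspofungin, anidulafungin, micafungin, and fluconazole", and these "will be presented both by treatment group and for treatment groups combined for subjects in the mITT population". It adds MIC50, MIC90 and range for CD101, caspofungin and fluconazole. Sections 5.3.3.3 to 5.3.3.5 then summarize overall success, mycological success and clinical cure by species and "MIC cutoff for CD101, caspofungin and fluconazole at Day 14", by treatment group. Neither place gives another rule for choosing the isolate.

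**The concern.** A baseline MIC is fixed before randomization and should have the same expected distribution in every arm. A selection rule keyed to the assigned drug breaks that for subjects with more than one eligible sample. In the CD101 arms the reported CD101 MIC is the highest among the subject's isolates. In the caspofungin arm it is the CD101 MIC of an isolate picked for a different drug. If caspofungin does the picking there, the caspofungin MIC is distorted the other way.

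Three things follow. By-arm MIC tables can show a difference that comes from the rule rather than the patients. The combined column mixes two kinds of selection. And the same patient could fall on different sides of a CD101 cutoff depending on the arm. In the comparator arm the rule also cannot be programmed as written, because it does not say whether caspofungin or fluconazole decides.

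**Working it through.** **Step 1: what study drug means.** The SAP has no formal definition, so its usage has to settle the question. Section 1.2.2 treats study drug as something assigned, whose identity is blinded. Section 1.2.1 calls the caspofungin infusion IV study drug. Section 5.2.1 refers to oral study drug, which is fluconazole in the comparator arm. Section 5.4 covers subjects given the wrong study drug. Where only the test agent is meant, as in Sections 5.1.7, 5.3.3.3 and 5.3.4, the SAP writes CD101. The consistent reading is the assigned drug.

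**Step 2: when the rule acts.** It needs two or more samples of the same type, with the same pathogen, within 96 hours before randomization. It changes a result only if the MICs of those samples differ. A subject with one sample, or with one blood and one sterile-site isolate, is untouched.

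**Step 3: size.** The SAP states no figure to reproduce and gives no MIC variability, so every input here is an assumption. Two arms were simulated with identical true MIC distributions (400,000 subjects per scenario):

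- log2 MIC = subject effect (SD 1 dilution) + isolate effect (SD *s* = 0.5 or 1), rounded to whole dilutions;
- within-subject correlation *ρ* between CD101 and caspofungin MICs of 0, 0.5 or 0.9;
- a share *f* of 25%, 50% or 100% of subjects with *k* = 2 or 3 eligible isolates.

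The CD101 arm keeps the isolate with the highest CD101 MIC and the caspofungin arm the one with the highest caspofungin MIC. The CD101 MIC of the kept isolate is compared, with a cutoff one dilution above the population mean.

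| Case | *f* | *k* | *s* | *ρ* | Shift in mean CD101 MIC (dilutions) | At or above cutoff, CD101 arm | At or above cutoff, caspofungin arm |
|---|---|---|---|---|---|---|---|
| Smallest | 25% | 2 | 0.5 | 0.9 | 0.02 | 35.0% | 34.4% |
| Middle | 50% | 2 | 1 | 0.5 | 0.15 | 44.1% | 39.8% |
| Largest | 100% | 3 | 1 | 0 | 0.85 | 60.7% | 36.2% |

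**Step 4: check by formula.** Without rounding, the expected shift is *f* × *s* × *c_k* × (1 − *ρ*), where *c_k* is the expected maximum of *k* standard normal values: *c_2* = 1/√π = 0.564 and *c_3* = 3/(2√π) = 0.846.

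- Largest: 1 × 1 × 0.846 × 1 = 0.846, matching 0.85.
- Middle: 0.5 × 1 × 0.564 × 0.5 = 0.141, against 0.15.
- Smallest: 0.25 × 0.5 × 0.564 × 0.1 = 0.007, against 0.02.

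The simulated figures exceed the formula when *ρ* is above 0 because rounding creates tied MICs, and the simulation then takes the first isolate. The SAP has no tie rule either. The formula also shows what matters: the shift disappears as *f* approaches 0 or *ρ* approaches 1.

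**Step 5: one rule in all arms.** If every arm selects in the same way, the expected difference between identical arms is 0 by construction.

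**The case against.** The case for leaving this as a minor clarification has real content.

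- **Reach.** The study is descriptive (Sections 3.1 and 3.7). Neither overall response at Day 14 nor mITT membership uses the MIC. This stands.
- **Frequency.** A reader might infer that most subjects have several isolates, because Section 1.2.5 requires another blood culture set when the qualifying one was drawn more than 12 hours before randomization. That set must be drawn, but it need not be positive. The mITT2 and mITT3 definitions in Section 2.1 single out, for blood, subjects positive within 12 hours before or 72 hours after randomization, so some mITT subjects are expected not to be. The share affected is unknown.
- **Visibility.** A reader might infer that CD101 MIC50 and MIC90 will plainly look higher in the CD101 arms. With 25% of subjects having 2 isolates, SD 0.5, correlation 0.5 and 10 subjects per arm, the mean MIC50 shift is 0.04 dilutions against a sampling SD of about 0.5. Section 5.1.7 reports these statistics only for species with at least 10 isolates with susceptibility data in each group, and Part A plans about 30 mITT subjects per group.
- **Worst case for the drug received.** Taking the highest MIC to the received drug is a defensible choice, and it already gives the maximum for CD101 in the CD101 arms and, if caspofungin decides, for caspofungin in its arm. The distortion lies mainly in the other cells, such as outcome by CD101 MIC among caspofungin subjects. This stands, but those cells and the combined column are planned output.
- **Blinding.** That the derivation needs treatment codes is not in itself a fault, since these tables are produced after lock and unblinding (Section 3.13).
- **Another reading.** If the sponsor meant CD101 in every arm, the arm difference disappears. The text does not say so, and its usage elsewhere points the other way.

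**Conclusion.** The point holds for subjects with several same-type, same-species baseline samples whose MICs differ. For them, Section 3.4 as written makes isolate selection depend on the assigned treatment, and the affected MIC tables do not compare like with like. The direction is systematic. The size cannot be derived from the SAP: 0.02 to 0.85 doubling dilutions spans the assumed inputs.

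A narrower and larger range should not be quoted. Giving every subject 2-3 isolates and holding the correlation at 0.5 or below yields 0.18 to 0.85, but nothing in the SAP supports either restriction, and CD101 is itself an echinocandin (Section 1.1.1), so a higher correlation with caspofungin cannot be excluded.

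The documents also do not support reading this as a bias in the efficacy results. It is confined to the descriptive MIC distributions, MIC50/MIC90/range and outcome-by-MIC tables. It still deserves correction, because the comparator-arm rule is ambiguous and the remedy costs almost nothing.

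**What to change.** In Section 3.4, remove the reference to study drug and state a rule that does not depend on treatment. For each drug's MIC table in Section 5.1.7, and for that drug's outcome-by-MIC table in Sections 5.3.3.3 to 5.3.3.5, use the highest MIC to that drug among the subject's eligible same-type baseline isolates of the species, in every arm. This removes the choice between caspofungin and fluconazole, and leaves the CD101 cells in the CD101 arms unchanged, as well as the caspofungin cells in the comparator arm if caspofungin was the intended selector. Ties no longer matter, because the tabulated value is the maximum itself.

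The cost is a sentence of SAP text and a small programming change, with no new data. The drawback is that the isolate used can differ between drug tables for the same subject, which a table footnote should say.
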